6.2 General Concomitant Medication and Supportive Care Guidelines

Carfilzomib is rapidly metabolized extra-hepatically by peptidase cleavage and epoxide hydrolysis with a short half-life of < 1 hour. Hence the potential for interactions with other drugs is minimal. However, because there is a marginal potential for interaction of carfilzomib with other concomitantly administered drugs through the cytochrome P450 system, the case report form must capture the concurrent use of all other drugs, over-the-counter medications, or alternative therapies. The Principal Investigator should be alerted if the patient is taking any agent known to affect or with the potential to affect selected CYP450 isoenzymes. Other agents known to be metabolized by the CYP3A system should also be captured since there is a possibility of interaction with carfilzomib. No carfilzomib dose adjustments or withholding of ongoing concurrent medications is suggested.

6.3 Duration of Therapy

Therapy will continue until progression (as defined below) or severe toxicities. Acyclovir will continue from day 1 of cycle 1 until ≥7 days after the last dose of carfilzomib. Androgen deprivation therapy with LHRH analogue or antagonist and bone protecting agent (denosumab or zoledronic acid) will also continue. If the bone protective agent has not already been initiated ≥4 weeks before trial registration, initiation of a bone protection agent is not allowed. CMP evaluations are performed on day 1 every 4 weeks,

CBC on days 1, 8 and 15 every cycle, and radiological evaluations are performed every 3 cycles or earlier if clinically indicated. Correlative studies include serial CTC enumeration (repeated on day 1 cycle 2, then q 3 cycles) and collection of whole blood is performed at baseline for 20S proteasome activity and other potential future correlative studies.

Progression of disease will be defined clinically as the first occurrence of any of the following and PSA progression alone will not constitute progression.

- 1) Two distinct new lesions on bone scan consistent with bone metastases in the best judgment of the investigator and confirmed by further new lesions on a subsequent scan ≥ 6 weeks later.
- 2) Progression in measurable disease as defined by RECIST criteria
- 3) Worsening of pain in the judgment of the investigator.
- 4) New bladder outlet or ureteral obstruction caused by cancer
- 5) New bone related events
 - a. Pathologic fracture
 - b. Spinal cord compression
 - c. Need for palliative radiation, surgery, or kyphoplasty to any neoplastic bone lesion
- 6) Deterioration of performance status to ECOG level 3-4
- 7) Death

Therapy is also discontinued for other non-progression events below:

- 1) Intercurrent illness that prevents further administration of treatment
- 2) Unacceptable adverse event(s)
- 3) Patient decides to withdraw from the study
- 4) General or specific changes in the patient's condition render the patient unacceptable for further treatment in the judgment of the investigator.

6.4 Duration of Follow Up

Patients will be followed for 4 weeks after removal from study or until death, whichever occurs first. Patients removed from study for unacceptable adverse events will be followed until resolution or stabilization of the adverse event, and subsequent progression or initiation of new therapy (whichever comes first).

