2.2 Secondary Objectives

- PSA changes (response, PSA decline $\geq 30\%$ within 3 months)
- CTC changes (unfavorable \rightarrow favorable, $>30\%$ decline)
- Measurable disease response rate (RECIST)
- Pain responses (decline in present pain index ≥ 2 , decrease in analgesics)
- Overall Survival

- Toxicities
- Association of outcomes with baseline whole blood 20S proteasome level

[figure not shown]

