6.5 Criteria for Removal from Study

Patients will be removed from study when any of the criteria listed in Section 6.3 applies. The reason for study removal and the date the patient was removed must be documented in the Case Report Form.

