8. STUDY CALENDAR

Baseline evaluations are to be conducted within 2 weeks prior to administration of protocol therapy. Scans and x-rays must be done ≤4 weeks prior to the start of therapy. In the event that the patient's condition is deteriorating, laboratory evaluations should be repeated within 48 hours prior to initiation of the next cycle of therapy.

	-28 days	-14 days (may serve as cycle 1 day 1 labs)	Day 1 (± 1 day) of every cycle (28 days)	Day 8 and 15 every cycle (± 1 day)	Day 1 Every 3 cycles	30 (± 7 days) post last treatment
ASSESSMENTS						
History and exam (H&P)	X		X			X ¹
ECOG performance status		X	X			X ¹
CBC with differential		X	X	X		X ¹
CMP		X	X			X ¹
PSA		X	X			X ¹
LDH		X				
Testosterone level		X				
Pain (PPI 0-5 scale)		X	X			X ¹
Analgesic intake (increased, decreased or stable)		X	X			X ¹
Echocardiogram	X		X ^{6,7}			
DISEASE ASSESSMENT						

CT chest , abdomen, pelvis	X				X	X ¹
Bone Scan	X				X	X ¹
TREATMENT						
Carfilzomib day 1,2, 8,9,15,16 (30 min IV infusion)			X ²	X ²		
Premedication (Dexamethasone, Acetaminophen)			X ³	X ³		
Pre-hydration (Normal saline 250-500 ml over 30 minutes)			X ⁴	X ⁴		
Acyclovir 400 mg PO bid			X ⁵	X ⁵		
LHRH analogue (if no prior orchiectomy)					X	
CORRELATIVE STUDIES						
CTC enumeration (3 time points)	X		X (cycle 2 only)		X (cycle 4 only)	
Whole Blood 20S proteasome assay	X					
FOLLOW-UP						
Disease progression and survival						X ¹

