Modest activity is considered clinically meaningful in this relatively heavily pretreated population with metastatic CRPC that has received abiraterone acetate and/or enzalutamide (prior chemotherapy and sipuleucel-T are allowed). The null hypothesis for this trial is that the primary endpoint of 6-month PFS <10% is not clinically meaningful and the alternative hypothesis is that the true clinical PFS of interest is $\geq 30\%$. Since we will follow all subjects for at least 6 months or until progression or death, we will not have censoring and 6 months PFS can be treated as a binomial random variable. With twenty five evaluable patients we will have 80% power for an exact binomial test at the one sided 0.05 significance level of the null hypothesis that the 6-month PFS rate is 10% if the actual rate is 30%. That null hypothesis will be rejected if 6 or more of the 25 subjects survive for 6 months progression free. Twenty-eight subjects will be accrued to allow for 10% inevaluable patients.

Sample Size/Accrual Rate

A total of 28 patients will be enrolled for this trial. Accrual period will be 6 to 12 months.

Analysis of Secondary Endpoints

The Kaplan-Meier method will be used to estimate PFS and OS rates over time with standard errors estimated using Greenwood's formula. Medians and their 95% confidence intervals will also be estimated. PSA response, PSA decline $\geq 30\%$ within 3 months, RECIST responses and regressions, pain response and CTC alterations will be analyzed as secondary endpoints. CTC changes will include changes from unfavorable ($\leq 5/7.5\text{ml}$) to favorable, and declines by $>30\%$. Pain response is defined as decline in present pain index ≥ 2 points and/or decrease in analgesics. Linear regression with PSA as the dependent variable and time as the dependent variable will be performed and used to estimate PSA DT. The association of baseline whole blood 20S proteasome level with PFS and other secondary endpoints will be examined using Cox regression to generate hypotheses for selecting suitable patients for further study.

Reporting and Exclusions

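### Follow-up stops about 4 weeks after progression, so the planned Kaplan-Meier overall survival would miss most deaths and probably read too high

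*Combined protocol and SAP*

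**What the plan says.** Section 2.2 lists "Overall Survival" among seven secondary objectives, and Section 1.4 names it as supportive evidence of efficacy. Section 10 gives the method: "The Kaplan-Meier method will be used to estimate PFS and OS rates over time", with Greenwood standard errors and medians with 95% confidence intervals. The Cox analysis of baseline 20S proteasome level covers PFS and the other secondary endpoints, so it would use the same OS data.

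Follow-up is set elsewhere:

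- Section 6.3: "Therapy will continue until progression (as defined below) or severe toxicities".
- Section 6.5: "Patients will be removed from study when any of the criteria listed in Section 6.3 applies". Progression is the main such criterion.
- Section 6.4: "Patients will be followed for 4 weeks after removal from study or until death, whichever occurs first".
- Section 8 has a calendar row headed "Disease progression and survival", marked only in the column for 30 (±7) days after last treatment and tied to footnote 1. That footnote extends follow-up only for patients who left without progressing, and ends at progression or new therapy. Sections 3.1 and 10 say the same.
- Section 10 gives a minimum: "Since we will follow all subjects for at least 6 months or until progression or death". This too ends at progression.

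PFS is defined in Section 11. OS has no definition, censoring rule or data cutoff.

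**The concern.** Under these rules a patient who progresses and is alive 4 weeks later is censored for OS at that point. Censoring therefore depends on progression, the event most closely linked to death in this disease. The people who carry the curve forward are those who have not progressed, or who did so within the last 4 weeks. Deaths later after progression, which should be the majority, are never recorded.

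The result is bias, not only loss of precision, and Greenwood intervals do not show it. The risk is practical. This is a single-arm trial whose background section cites median OS of 8.3 to 12.5 months in comparable patients. A reader setting an inflated median beside those figures could infer a survival gain that the follow-up rule created.

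**Working it through.** **The plan's own figure.** The only sample-size calculation is for 6-month PFS, and it reproduces. With 25 patients and rejection at 6 or more, the exact binomial gives P(X ≥ 6 | 0.10) = 0.0334 and P(X ≥ 6 | 0.30) = 0.8065. Allowing 10% inevaluable, 25/0.9 = 27.8, rounded up to 28. No event count or precision is stated for OS.

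**Inputs.**
- Window after progression: w = 28 days = 0.92 months (Section 6.4), with removal taken to occur at progression.
- Hazard of a first PFS event, exponential: λ = −ln(0.30)/6 = 0.2007 per month (design alternative; median 3.45 months).
- Median OS 8.3, 10.6 or 12.5 months (Section 1.1).
- Assumed: a share q of first PFS events are deaths (0, 10% or 20%), and survival after progression is exponential with hazard μ, set to give the chosen median OS.

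**Share of deaths observed** = q + (1 − q)(1 − e^(−μw)).

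Middle case (q = 0.10, median OS 10.6 months, mean post-progression survival 9.03 months, μ = 0.1107): 0.10 + 0.90 × (1 − e^(−0.102)) = 0.187, or 5.2 of 28.

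**What Kaplan-Meier estimates.** Beyond 4 weeks, the ratio of recent progressors to non-progressors at risk is r = (1 − q)λ(e^((λ−μ)w) − 1)/(λ − μ) = 0.173. The hazard that the curve picks up is (qλ + μr)/(1 + r) = (0.0201 + 0.0192)/1.173 = 0.0335 per month. Then e^(−12 × 0.0335) = 0.67. The simulation (400,000 patients) gave 0.674, with a median of 21.0 months.

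**Truth.** S(12) = e^(−12λ) + (1 − q)λ/(λ − μ) × (e^(−12μ) − e^(−12λ)) = 0.090 + 2.007 × (0.265 − 0.090) = 0.44, with a median of 10.6 months.

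At 12 months, 28 × 0.090 × 1.173 ≈ 3 patients remain at risk, before any other loss. In 59% of simulated 28-patient trials the median was not reached.

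**Sensitivity at the design alternative**, with median post-progression survival of 4 to 9 months:

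| Share of first PFS events that are deaths | Deaths seen of 28 | 12-month OS, Kaplan-Meier | 12-month OS, true |
|---|---|---|---|
| 0% | 1.9–4.1 | 0.73–0.87 | 0.35–0.59 |
| 10% | 4.5–6.5 | 0.61–0.71 | 0.32–0.54 |
| 20% | 7.1–8.9 | 0.51–0.58 | 0.30–0.49 |

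**Wider grid**: median PFS 1.81 (the null), 3.45 or 4.5 months (the last cited in Section 1.1), by the three OS medians and three values of q, 27 scenarios in all. Deaths observed run from 6% to 34% (1.8 to 9.6 of 28), and median observed follow-up from 2.5 to 5.4 months. OS is overstated at 6 and 12 months in 25 of 27.

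**When the direction reverses.** The curve is too high when μ exceeds qλ, that is, when the hazard of death is greater after progression than before it. At the null λ = 0.3838, so with q = 0.20, qλ = 0.077. Mean post-progression survival of 16.47 and 20.67 months (median OS 10.6 and 12.5) gives μ = 0.061 and 0.048, both lower. Those are the two exceptions: 12-month OS reads 41% against 46%, and 43% against 51%.

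**The case against.** The strongest case on the other side has four parts.

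- **Importance.** OS here is descriptive, one of seven secondary objectives in a 28-patient single-arm trial, with no hypothesis, comparator or decision rule. The go/no-go rule rests on 6-month PFS. This stands: the point concerns one secondary result, and calling the repair mandatory is on the strict side.
- **Intent.** The calendar row names survival, so the authors evidently meant to collect it, and sites may do so informally. But the row is tied to the 30-day column and to a footnote that ends at progression or new therapy. Informal collection is not provided for and would probably be uneven.
- **Size and direction.** The largest gaps assume that no first PFS event is a death, although Section 10 counts death as such an event. The 10% and 20% rows are the fairer guide. The 9-month post-progression assumption with no first-event deaths also takes true median OS to about 14 months, above the cited 12.5. Upward bias is the expected direction, not a certainty. Survival at 6 months suffers less: at 20% deaths it reads 0.71–0.76 against 0.61–0.73.
- **The censoring clock.** Section 6.4 counts from removal, and bone-scan progression needs confirmation at least 6 weeks later. If removal always waited for that, the window would be about 10 weeks. At the alternative with 10% deaths this gives 7 to 11 deaths seen and 12-month OS of 0.47–0.64 against 0.32–0.54. The bias shrinks but stays upward, and most deaths are still missed.

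**Conclusion.** The concern holds. As written, the follow-up rules cannot support the planned OS rates, median or confidence interval. That most deaths go unobserved is true in every scenario examined. Overstatement is the likely consequence: in the middle case 67% against 44% at 12 months, and a median of 21.0 against 10.6 months. It occurs whenever the risk of death is higher after progression than before. The exact size depends on exponential times, the assumed share of first events that are deaths, and background OS taken from other studies. The gap in the text depends on none of these. The Cox analysis of 20S proteasome level against OS inherits the problem. The primary 6-month PFS test does not.

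**What to change.** Amend Section 6.4, the calendar row and footnote 1 so that vital status is collected after removal for any reason, including progression and new therapy. Record review or a telephone call, for example every 3 months, is enough. Continue until death, withdrawal of consent or a stated cutoff such as 12 months after the last patient starts. In Section 10, define OS as time from start of treatment to death from any cause, censored at the date last known alive.

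With 12 months of uniform accrual, exponential OS and that cutoff, each patient has 12 to 24 months of potential follow-up. With monthly hazard h = ln 2/median, the expected share of deaths seen is 1 − (e^(−12h) − e^(−24h))/(12h): 62% at a median of 12.5 months and 77% at 8.3 months, about 17 to 22 of 28.

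The cost is a short amendment and a few checks on 28 patients, with no added procedures. If this is not done, remove the OS rates, the median and the OS part of the Cox analysis, or label the curve as survival while under study observation and say that it does not estimate OS.

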This is a multi-center one-stage phase II trial conducted at UAB Comprehensive Cancer Center and outside sites, and managed by the CTNMO (Clinical Trial Network Monitoring Office) housed at the UAB Comprehensive Cancer Center. Clinical PFS as the primary end-point and the trial will enroll 28 patients. The eligible population includes men with metastatic castration-resistant prostate cancer (CRPC) who have received prior abiraterone and/or enzalutamide (prior chemotherapy is allowed). Carfilzomib is administered twice-weekly on consecutive days (± 1 day) (days 1, 2, 8, 9, 15, 16) as a 30 minute intravenous (IV) infusion for 3 weeks every 4 weeks (1 cycle) with dexamethasone and acetaminophen premedication as well as normal saline 250 ml over 30 minutes as pre-hydration. The dose of carfilzomib is 20 mg/m² on days 1 and 2 of cycle 1 and then escalated in succeeding weeks and cycles to 56 mg/m² for no dose limiting toxicities (DLTs) occur defined as any grade ≥ 3 non-hematologic toxicity or grade ≥ 4 neutropenia or thrombocytopenia lasting ≥ 7 days.

Acyclovir 400 mg orally twice daily is required during therapy, which may be discontinued ≥ 7 days after the last dose of carfilzomib. Therapy will continue until progression (as defined below) or severe toxicities. Patients removed from the trial for toxicities or other reasons will continue to be followed until progression or starting a new agent. Androgen deprivation therapy with LHRH analogue or antagonist and bone protecting agent (denosumab or zoledronic acid) will also continue. Comprehensive metabolic panel (CMP) evaluations are performed on day 1 every 4 weeks, complete blood cell (CBC) counts on days 1, 8 and 15 every cycle, and radiological evaluations are performed every 3 cycles or earlier if clinically indicated. Pain (PPI score, Appendix B) and analgesic intake (Appendix C) are recorded on day 1 of every cycle. Correlative studies include serial CTC enumeration (repeated on day 1 cycle 2 and day 1 cycle 4) and collection of whole blood is performed at baseline for 20S proteasome activity. Progression of disease will be defined clinically as the first occurrence of any of the following, and PSA progression alone will not constitute progression:

- 1) Two distinct new lesions on bone scan consistent with bone metastases in the best judgment of the investigator and confirmed by further new lesions on a subsequent scan ≥ 6 weeks later.

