³Dexamethosone dose is 4 mg PO/IV with carfilzomib 20 mg/m² and 8 mg PO/IV with carfilzomib 56 mg/m², dexamethasone may be discontinued from cycle 2 day 1 if patient is tolerating carfilzomib therapy per investigator discretion and/or has adverse effects from dexamethasone, acetaminophen dose is 650 mg PO x 1

⁴Prehydration with 250-500 ml of normal saline is given during cycle 1 and may be discontinued from cycle 2 day1 per investigator discretion (post-hydration with 250-500 ml normal saline is optional per investigator discretion)

⁵Acyclovir to start on day 1 of cycle 1 and stop ≥7 days after last dose of carfilzomib

⁶Only if clinically indicated for patients who develop CHF on study

⁷Multigated Acquisition Scan (MUGA) is acceptable

STATISTICAL CONSIDERATIONS

Modest activity is considered clinically meaningful in this population with mCRPC that has received abiraterone acetate and/or enzalutamide (with prior chemotherapy and sipuleucel-T allowed). The null hypothesis for this trial is that the primary endpoint of 6-month PFS <10% is not clinically meaningful and the alternative hypothesis is that the true clinical PFS of interest is ≥30%. Since we will follow all subjects for at least 6 months or until progression or death, we do not expect any censoring. Thus 6 month PFS can be treated as a binomial random variable. With twenty five evaluable patients we will have 80% power for an exact binomial test at the one sided 0.05 significance level of the null hypothesis that the 6-month PFS rate is 10% if the actual rate is 30%. That null hypothesis will be rejected if 6 or more of the 25 subjects survive for 6 months progression free. Twenty-eight subjects will be accrued to allow for 10% inevaluable. The Kaplan-Meier method will be used to estimate PFS and OS rates over time with standard errors estimated using Greenwood's formula. Medians and their 95% confidence intervals will also be estimated. PSA response, PSA decline ≥30%, RECIST responses and regressions, pain response and CTC alterations will be analyzed as secondary endpoints. The association of baseline whole blood 20S proteasome level with PFS and other secondary endpoints will be examined using Cox regression to generate hypotheses for selecting suitable patients for further study.

TABLE OF CONTENTS

TITLE PAGE

SYNOPSIS

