10. STATISTICAL CONSIDERATIONS

Study Design/Endpoints

This is a 2-center one-stage non-randomized phase II trial conducted at UAB Comprehensive Cancer Center and outside sites. Clinical PFS as the primary end-point and the trial will enroll 28 patients. The eligible population includes men with metastatic CRPC who have received prior abiraterone and/or enzalutamide (prior chemotherapy and sipuleucel-T are allowed). Therapy will continue until progression (as defined below) or severe toxicities. Patients removed for reasons other than progression will continue to be followed until progression or initiation of another agent. Correlative studies include serial CTC enumeration (day 1 of cycles 1, 2 and cycle 4) and collection of whole blood is performed at baseline for 20S proteasome activity. Progression of disease will be defined clinically as the first occurrence of any of the following, and PSA progression alone will not constitute progression:

- 1) Two distinct new lesions on bone scan consistent with bone metastases in the best judgment of the investigator and confirmed by further new lesions on a subsequent scan ≥ 6 weeks later.
- 2) Progression in measurable disease as defined by RECIST criteria
- 3) Worsening of pain in the judgment of the investigator.
- 4) New bladder outlet or ureteral obstruction caused by cancer

- 5) New bone related events
 - a. Pathologic fracture
 - b. Spinal cord compression
 - c. Need for palliative radiation, surgery, or kyphoplasty to any neoplastic bone lesion
- 6) Deterioration of performance status to ECOG level 3-4
- 7) Death

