Pain response and progression

Patients with a PPI score of at least 2, or need for analgesics, or both at baseline are assessed for the pain response. A pain response is defined as a two-point reduction in the PPI score from baseline without an increase in the analgesic use or as a reduction in analgesic use without an increase in the PPI score. Pain progression is defined as an increase in the PPI score of at least one point from the nadir, an increase in analgesic use, or a requirement for palliative radiotherapy.

Progression-Free Survival

PFS is defined as the duration of time from start of treatment to time of progression or death, whichever comes first.

12. **CORRELATIVE STUDIES**

Circulating Tumor Cell (CTC) enumeration will be used as a secondary marker for efficacy of response to the treatment. Baseline CTC will be obtained prior to initiation of therapy and day 1 of cycles 2 and 4. Baseline whole blood 20S proteasome activity will also be determined.

CTC enumeration

The CELLSEARCH[®] System led to the first standardized, FDA-cleared semi-automated system that detects and enumerates CTCs of epithelial origin (CD45-, EpCAM+, and cytokeratins 8, 18+, and/or 19+) from a 7.5-mL blood sample with high sensitivity and specificity. The CELLSEARCH[®] System uses unique immunomagnetic and fluorescence imaging technology to provide rapid and reproducible analysis of CTCs with a simple 3-step process: sample collection, sample preparation, and sample analysis. System components include:

- Proprietary CellSave Preservative sample tubes
- CELLSEARCH[®] CTC Test and Control kits
- Automated CELLTRACKS[®] AUTOPREP[®] System
- CELLTRACKS ANALYZER II[®]

CellSave Preservative tubes provide an optimized cell preservative that stabilizes CTCs for up to 96 hours at room temperature, which allows shipment of samples to remote locations for analysis and improves the reproducibility and reliability of CTC analysis. CTCs are fragile and tend to degrade within a few hours when collected in standard evacuated blood collection tubes.

Once the blood sample is collected for UAB patients, the tube will be delivered to UAB main laboratory to be sent out to Quest Diagnostics for CTC enumeration. For outside sites, the tube will be sent directly to Quest Diagnostics for CTC enumeration.

Whole Blood 20S Proteasome Activity

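### Section 6.4 stops follow-up 4 weeks after most non-progression removals, against the rest of the protocol; neither follow-up rule guarantees the 6-month status the primary test needs, and the rule for unknown outcomes is not extended to PFS

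*Combined protocol and SAP*

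**What the plan says.** Section 6.4 gives a general rule, "Patients will be followed for 4 weeks after removal from study or until death, whichever occurs first", and one exception: "Patients removed from study for unacceptable adverse events will be followed until resolution or stabilization of the adverse event", and after that until progression or new therapy.

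The other sections are broader. The synopsis and Section 3.1 say "Patients removed from the trial for toxicities or other reasons will continue to be followed until progression or starting a new agent". Section 10 says "Patients removed for reasons other than progression will continue to be followed until progression or initiation of another agent". Footnote 1 to the Section 8 calendar has the same rule and adds a schedule: clinical assessments about every 28 days and imaging about every 90 days.

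The primary analysis rests on a stronger statement in Section 10: "Since we will follow all subjects for at least 6 months or until progression or death, we will not have censoring". The synopsis is a little softer: "we do not expect any censoring". On that basis 6-month PFS is tested as a binomial proportion (10% against 30%, exact one-sided 0.05 test, 25 evaluable, reject at 6 or more), with 28 enrolled to allow for 10% inevaluable.

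The endpoint definition in Section 11 is "PFS is defined as the duration of time from start of treatment to time of progression or death, whichever comes first". Under Reporting and Exclusions, Section 10 has a category for patients whose outcome cannot be assessed and counts it as treatment failure in the analysis of response rate. It also bases conclusions on all eligible patients.

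**The concern.** Section 6.3 lists reasons for stopping that are neither progression nor an adverse event, for example "Intercurrent illness that prevents further administration of treatment". For these patients the two follow-up rules conflict, and a site that consults the section headed as the follow-up section would stop after 4 weeks.

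Resolving the conflict in favour of the longer rule does not fully rescue the no-censoring statement. That rule stops at a new agent, which is not a progression criterion in Section 10 and not a PFS event in Section 11. A patient who switches at month 4 without progression therefore leaves follow-up with an unknown 6-month status.

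A binomial count needs a yes or no for each patient. If some are unknown, the result depends on how they are counted. In an open-label single-arm trial, that choice should be fixed before the data are seen.

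**Working it through.** **When 6.4 falls short.** Take 6 months as day 183. Four weeks of follow-up reaches day 183 only if removal is on or after day 183 − 28 = 155. Cycle 6 starts on day 5 × 28 + 1 = 141, so day 155 is cycle 6 day 15. An earlier removal for a reason other than an adverse event or progression can leave the endpoint unobserved under 6.4.

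**The plan's own figure.** With X ~ Binomial(n, p), Section 10 gives n = 25, cutoff 6, p = 0.10 and 0.30.
- Type I error: P(X ≥ 6 | 25, 0.10) = 0.033
- Power: P(X ≥ 6 | 25, 0.30) = 0.807
- A cutoff of 5 would give type I error 0.098, so 6 is right for 25.

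The stated design reproduces when all 25 statuses are known.

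**Can the counting rule decide the result?** Suppose that, of 25 patients, 5 are progression-free, 18 have progressed and 2 are unknown (an invented case near the cutoff). One-sided p-values against 10%:

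| Treatment of the 2 unknowns | Count | p |
|---|---|---|
| Both failures | 5/25 | 0.098 |
| Excluded | 5/23 | 0.073 |
| One progression-free | 6/25 | 0.033 |
| Both progression-free | 7/25 | 0.0095 |

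The first two do not reject; the last two do.

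**Cutoff by number analysed.** The smallest cutoff with exact type I error at or below 0.05:

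| n | Cutoff | Type I error | Power |
|---|---|---|---|
| 25 | 6 | 0.033 | 0.807 |
| 26 | 6 | 0.040 | 0.837 |
| 27 | 6 | 0.047 | 0.864 |
| 28 | 7 | 0.018 | 0.780 |

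A cutoff of 6 applied to 28 would have type I error 0.055.

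**Power when unknowns count as failures.** If m patients are observed, power is P(X ≥ cutoff | m, 0.30).
- Cutoff 6: 0.807 with 25 observed, 0.771 with 24.
- Cutoff 7 with 28 analysed: 0.780 with none unknown, 0.659 with 3 unknown (25 observed).

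**How many might be unknown?** The plan gives no rate for this trial. Section 1.3 reports that 6 of 47 patients with solid tumors or lymphoma stopped carfilzomib early for reasons other than progression or adverse events. If that applied here (assumption): 6/47 × 28 = 3.6 patients. Two of the six, one with brain metastases and one with severe bone pain and declining performance, would plausibly be progression under this protocol. That leaves 4/47 × 28 = 2.4. These are treatment stops, and not all of them need lead to an unknown status. No figure is given for new agents started before progression.

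**The case against.** Section 6.4 is the outlier. The longer rule stands in four places, including the calendar that sets the visits and the statistics section, so many sites would follow it. That is fair, but it leaves the new-agent gap open.

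Four stronger readings are tempting, and the documents do not support them.

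- *The plan is silent on unknown outcomes.* It is not. Section 10 counts the not-assessable category as treatment failure and equates that with progression. But the sentence governs response rate and leaves the precise definitions to the protocol, while the allowance for inevaluable patients points towards exclusion. The gap is that the rule was not carried over to 6-month PFS.
- *Over a quarter of patients could be lost.* Section 1.3 reports 13 of 47 (27.7%) stopping for adverse events, or 13/47 × 28 = 7.7 of 28. That is the group 6.4 already follows to progression or new therapy, so it is the wrong proxy for the 4-week limit.
- *The type I error is 0.055, or the sample size is wrong.* The 0.055 arises only if the 25-patient cutoff is applied to 28, which the plan does not say to do. The exact test at 0.05 determines the cutoff for any n.
- *Everyone should be followed through a new agent and scored at 6 months.* With no control arm, this credits carfilzomib with the next drug's effect. For illustration, if the true rate is 10% and 2 patients switch with an assumed 50% chance of being progression-free at 6 months, type I error rises from 0.033 to 0.090 at 6 of 25, and from 0.018 to 0.051 at 7 of 28.

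**Conclusion.** The concern holds as a conflict between sections and an incomplete counting rule for the primary endpoint. Section 6.4 contradicts the synopsis and Sections 3.1, 8 and 10 for removals that are not due to adverse events. Neither rule delivers the complete 6-month status on which Section 10 relies, and the existing treatment of unknown outcomes is not extended to PFS. The sample size calculation is sound.

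The likely size is modest. On the assumption that the 6-of-47 figure carries over, about 2.4 to 3.6 of 28 patients would stop for other reasons, close to the 3-patient allowance. With the cutoff of 6, having 25 observed keeps power at 0.807 and losing one more costs about 3.5 points (0.807 − 0.771). The effect on the conclusion is larger only if the count falls near the cutoff, as in the invented case. The correction should be made because it is cheap and must precede the data.

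**What to change.** 1. **Section 6.4, first sentence.** Replace it with the footnote 1 rule: every patient who stops carfilzomib without progression, for any reason, is followed on that schedule until progression, death or new therapy. Keep the follow-up of adverse events to resolution.
2. **Section 10, and the matching synopsis text.** Replace the no-censoring statement with a counting rule: an eligible treated patient who starts a new anticancer agent before 6 months without progression, or whose 6-month status is unknown (for example after withdrawing consent), counts as not progression-free in the exact binomial test.
3. **Section 10, decision rule.** State that the cutoff follows from the exact one-sided 0.05 test for the number analysed: 6 for 25, 26 or 27 patients and 7 for 28.

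This is wording only and needs no visits beyond those already in the calendar. The price is power. With a cutoff of 6, power is at least 0.807 while 25 or more are observed and 0.771 with 24. If all 28 are analysed the cutoff is 7, and power is 0.780 with none unknown and 0.659 with 3. The sponsor should accept that last figure knowingly. The rule also scores a patient who switches early because of toxicity as a failure, which is conservative for a single-arm activity trial.
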